#### **5.3.2 TARGET POPULATION**

HCPs across the UK involved in the care of women with A-POP who are eligible for surgery/have received surgery previously, those who would be involved in a potential future trial, including but not limited to, doctors of various specialities and grades, nurses in various roles such as practice nurses, advanced gynaecology and urogynaecology nurse specialists.

#### 5.3.3 SAMPLE SIZE

Anticipated 20-30 participants. Justification for sample size: Numbers will remain flexible to ensure that

the overall sample and associated data have sufficient information power to develop new knowledge in relation to the research questions(40). This approach will also help identify if we can engage and recruit from multiple sites, in different UK locations, for any future RCT.

#### 5.3.4 SAMPLING AND RECRUITMENT

HCPs will be recruited via a range of pathways to facilitate diversity and heterogeneity in characteristics and skillset, and to ensure that we can achieve our recruitment targets. These include: (1) HCPs identified from across the UK complex uro-gynaecology centres performing SSF and/or colpocleisis surgery including the anticipated eight recruitment sites involved in WPs 1 and 3; (2) the C-POP study teams' personal and professional networks; (3) snowballing; (4) advertising on social media, and (5) appropriate mailing lists such as BSUG and RCOG. Maximum variation sampling will include type of centre, numbers of surgeries performed, level of experience, surgical vs. non-surgical HCPs, and location/geographical spread **[Core element 1: Context]**. Potential HCP participants who see online study advertising will also have the option of completing an online eligibility screening survey. The online eligibility screening survey will capture their contact preferences, and indicate eligibility for potential study participation. Maximum variation within the sample will be routinely reviewed (e.g., at the fortnightly project team meetings). Participants will be offered a £25 voucher to thank them for their time.

#### 5.3.5 ELIGIBILITY

(*i*) Inclusion criteria: UK based secondary care HCPs involved in the care of women with A-POP (either currently or within the last 5 years); working in a UK complex uro-gynaecology centre; able to give informed consent and speak English. (*ii*) Exclusion criteria: HCPs based in primary care. **Rationale for eligibility** criteria: This sample ensures data are gathered from HCPs who would likely be involved in a future effectiveness trial.

#### 5.3.6 CONSENT

As per work package 1.

#### 5.3.7 DATA COLLECTION

Phone, video conference or face to face semi-structured interviews will be conducted (as for WP1) to explore: (i) acceptability of the treatment options for HCPs; (ii) acceptability of the proposed trial processes for HCPs, including their willingness to accept randomisation of patients in their care; (iii) feasibility of trial delivery and collection of data on the resource use and costs associated with treatment options; and (iv) issues related to equipoise when discussing options with patients [Core element 4: Uncertainties; Core element 6: Economics]. Additional issues to be explored include HCP perceptions of which patients are

eligible for colpocleisis; barriers and facilitators to being involved in a trial; potential primary and secondary outcomes and meaningful progression criteria. Participants will be given the choice to see the interview question list in advance of participation, allowing participants to familiarise themselves with the main topics for discussion and raise any queries with the team in advance of the interview.

#### 5.3.8 DATA ANALYSIS:

Data will be analysed as for WP1 (except for translation as all interviews will be in English).

# 5.4 Work package 3: Quantitative cross-sectional study exploring the potential number of eligible women for an effectiveness trial (objective 4)

#### 5.4.1 DESIGN:

Cross sectional study.

#### 5.4.2 TARGET POPULATION:

Women and individuals assigned female at birth (AFAB), who have been diagnosed with A-POP and who are eligible for colpocleisis and SSF (see section 5.4.5).

#### 5.4.3 SAMPLE SIZE:

Comprehensive account of relevant clinical activity over a 6-month period.

#### 5.4.4 SAMPLING AND RECRUITMENT:

Potential participants will be identified from an anticipated eight diverse recruiting sites from UK complex uro-gynaecology centres performing A-POP surgery and who reported data to BSUG 2019-2022 as per WP1.

#### 5.4.5 ELIGIBILITY

All females (or AFAB) age 18 years and above, diagnosed with A-POP and eligible for both colpocleisis and SSF procedures (i.e., no longer intend to have penetrative vaginal intercourse and who are willing to have either surgical procedure) will be included. *Rationale for eligibility criteria:* This sample ensures we gather data to inform feasibility of recruiting to a future effectiveness trial. We do not intend to screen for potential exclusion criteria at this stage.

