## 1 Background and Rationale

Pelvic organ prolapse (POP) affects 1 in 2 women(1). Apical pelvic organ prolapse (A-POP) is where the uterus, cervix, or vaginal vault bulge or hang down into the vagina. Incidence peaks at 70-79 years and negatively impacts quality of life(2). For older women with A-POP, the National Institute for Health and Care Excellence (NICE) recommends non-surgical management as first line treatment(3). If these are ineffective, surgical intervention should be considered. Surgical options for older women with A-POP are: sacrocolpopexy (performed abdominally), sacrospinous fixation ((SSF) performed via a vaginal route) and colpocleisis (performed via a vaginal route). This research focusses on SSF and colpocleisis as they are performed via a vaginal route and not sacrocolpopexy as this is performed abdominally. Although colpocleisis has lower complication and recurrence rates than SSF, it is an obliterative surgery which removes the ability to have penetrative vaginal intercourse(4). A British Society of Urogynaecology (BSUG) audit reported that SSF is associated with short term complications including: readmission within 30 days of surgery (4.4%), catheterisation for >10 days (3.1%) and return to theatre within 72 hours of surgery (0.8%)(5). The number of SSF and colpocleisis procedures has increased year on year, with almost four times as many SSFs compared to colpocleisis in 2021 (860 vs. 186 respectively)(6). To date there is no evidence to say why colpocleisis is undertaken less commonly but possible explanations include: lack of equipoise of clinicians; that colpocleisis is 'end-of-the-road' surgery; uneasiness with obliterative surgery; or unfamiliarity with the surgical technique. Given the uncertainties, this is an opportune moment to compare the effectiveness and cost-effectiveness of colpocleisis compared to SSF via a randomised controlled trial (RCT). However, views of key stakeholders are needed to explore if a future effectiveness trial is feasible and acceptable.

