#### 4.2 Objectives

- To explore the feasibility and acceptability of the interventions and a future effectiveness study with eligible women and HCPs (WP1,2) [Core elements 1, 3 & 4: Context, Stakeholders & Uncertainties]
- (2) To identify and explore the key uncertainties for eligible women and HCPs regarding surgical procedures for A-POP (WP1,2) [Core elements 3 & 4: Stakeholders & Uncertainties]
- (3) To identify and explore sensitivities and preferences for eligible women and HCPs regarding equipoise for A-POP treatment options (WP1,2) [Core elements 2, 3 & 4: Programme theory, Stakeholders & Uncertainties]
- (4) To estimate the number of women who will be eligible to participate in a future effectiveness study(WP3) [Core element 4: Uncertainties]
- (5) To develop a programme theory and provide key design recommendations for a future effectiveness and cost-effectiveness study comparing colpocleisis and SSF for women with A-POP (WP4) [Core elements 3, 5 & 6: Stakeholders, Refinement & Economics]

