#### 5.4.6 DATA COLLECTION

Members of the women's direct care team will collect anonymised data on women meeting the eligibility criteria via scrutiny of referral letters and clinic notes. Sites will be asked to report these data a minimum of

once a month during the six-month data collection window, but can do this at a frequency (e.g., weekly, every two weeks) that suits their local clinical set up and resources. Data will be recorded in an anonymous screening log/proforma and sent securely to the C-POP research team at University of Birmingham. As part of the site initiation visits and study set up, the C-POP research team will work with the site to establish the best ways to record and send these data. Demographic information available in notes (e.g., age, ethnicity, first half of postcode (as a marker of deprivation) and first language) will also be collected to enable characterisation of the potential trial population.

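### WP3 defines eligibility by what a woman intends and would accept, but reads it only from letters and notes, so its count cannot separate ineligible from not documented

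*Protocol*

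**What the plan says.** Protocol section 5.4.5 includes adults with apical prolapse (A-POP) who are eligible for both operations. It explains this as women who "no longer intend to have penetrative vaginal intercourse and who are willing to have either surgical procedure". It also states: "We do not intend to screen for potential exclusion criteria at this stage".

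Section 5.4.6 asks members of the direct care team to "collect anonymised data on women meeting the eligibility criteria via scrutiny of referral letters and clinic notes". On the form of the record it says: "Data will be recorded in an anonymous screening log/proforma". At site set-up, "the C-POP research team will work with the site to establish the best ways to record and send these data". Age, ethnicity, part of the postcode and first language are also taken from the notes, to describe the potential trial population.

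Section 5.4.3 sets no target number and asks for a full account of six months' activity. Section 5.4.7 summarises the data descriptively and uses them to model a UK-wide number for a future randomised trial. This serves objective 4 in section 4.2: "To estimate the number of women who will be eligible to participate in a future effectiveness" study.

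**The concern.** The definition and the data source do not match. Whether a woman still intends penetrative intercourse, and whether she would accept either operation, are things only she can say. The source is what someone happened to write about her. The text does not require anyone to ask her, gives no rule for notes that are silent, and describes no record for women who do not qualify.

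A low count could then mean few eligible women, or few notes that mention the two items. Those readings point to different conclusions about whether a trial can recruit. Objective 4 is the study's only quantitative objective, and the demographic profile of the potential trial population comes from the same log, so it is exposed to the same problem. An analysis plan cannot repair this later: the log is anonymous, and information that was never recorded cannot be recovered.

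**Working it through.** WP3 states no expected count, precision or power, so there is no figure to reproduce. The check has two parts.

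**Part 1: the sections side by side**

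| Step | Section | Content |
|---|---|---|
| Definition | 5.4.5 | Two states of the woman: intention and willingness |
| Source | 5.4.6 | Referral letters and clinic notes |
| Who is recorded | 5.4.6 | Women meeting the criteria; no screened denominator stated |
| Silent notes | 5.4.5 to 5.4.7 | No rule and no category |
| Use | 5.4.7 | UK-wide projection |

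Section 1.1.3 gives two reasons to expect gaps or errors in the notes. It says that speaking about sexual activity may be seen negatively, in a passage on culture and religion, so gaps may differ between patient groups. It also reports from patient involvement that many women may not be having intercourse before surgery because of their prolapse symptoms. A note of current inactivity is therefore not evidence of future intention, and inferring one from the other would add women wrongly. WP1 and WP2 explore preferences by interview, but nothing links them to the WP3 log or calibrates it.

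**Part 2: illustration with assumed rates**

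The documents give no documentation rate, so every rate here is an assumption. Let d1 and d2 be the probabilities that intention and willingness are written down for a truly eligible woman. If the two are independent, the share of eligible women captured is d1 × d2.

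| d1 = d2 | Captured |
|---|---|
| 30% | 0.3 × 0.3 = 9% |
| 50% | 0.5 × 0.5 = 25% |
| 70% | 0.7 × 0.7 = 49% |
| 90% | 0.9 × 0.9 = 81% |

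Two sites with the same true number, one at 90% per item and one at 50%, would report counts in the ratio 0.81 / 0.25 = 3.24. If the two items were always written down together, capture would be 90% against 50% and the ratio 0.9 / 0.5 = 1.8.

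Error can also run upward. Assume 400 women with A-POP, of whom 100 are truly eligible, and let a share f of the other 300 be counted wrongly. The count is 100 × capture + 300 × f.

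- Capture 25%, f = 5%: 25 + 15 = 40.
- Capture 49%, f = 20%: 49 + 60 = 109.
- Capture 81%, f = 20%: 81 + 60 = 141.

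The same true figure of 100 can thus appear as 40 or 141. The planned log holds nothing that would show which case applies.

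**The case against.** The strongest reply is that practice may be better than the text. The people reading the notes are the women's own care team, who may know more than the notes hold. A proforma exists, its fields are not shown, and recording is to be settled with each site. WP3 elsewhere speaks of potential or likely eligibility, and its results go to the stakeholder event together with those of WP1 and WP2. All of this is fair and limits the severity. It does not remove the point, because the text secures no common handling of silent notes and describes data only for women who qualify.

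Several stronger readings are tempting and are not supported:

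- **That silent notes count as ineligible.** Section 5.4.6 does not say so. It gives no rule.
- **That the count will be low wherever clinicians lack equipoise.** Section 1 offers "uneasiness with obliterative surgery; or unfamiliarity with the surgical technique", along with lack of equipoise, only as possible explanations for fewer colpocleisis operations. It says nothing about what clinicians discuss or record.
- **That the audit figures bound the error.** Section 1 gives 186 colpocleisis and 860 SSF procedures in 2021. One could form 186 + 860 = 1,046 and 1,046 / 186 = 5.6. That compares numbers of operations, not documentation. Nor are these valid bounds: in one SSF series cited in section 1.1.3, 55% were sexually active before surgery, and a woman who chose colpocleisis need not have been willing to have either procedure.
- **That leaving out exclusion criteria is a hidden upward bias.** Section 5.4.5 discloses it. Only the description of the result needs care.
- **That the log should test the statement in section 5.2.2 that colpocleisis-eligible women are also SSF-eligible, or record clinicians' willingness to randomise.** The first is not a WP3 aim, and WP2 explores the second (section 5.3.7).

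**Conclusion.** The point holds as a mismatch between definition and data source. Followed as written, WP3 produces a count that mixes true ineligibility with non-documentation, possibly unevenly by site and patient group, and then projects it to the UK. The size and direction of the error cannot be determined from the documents. The 25% against 81% capture figures show only how sensitive the count could be, and rest on assumed recording rates of 50% and 90% per item and on independence. Whether the effect is large in practice is unknown. This should be fixed, because it is cheap at the design stage and cannot be recovered at analysis. It does not invalidate the study.

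**What to change.** In sections 5.4.5 and 5.4.6, log every woman with A-POP whose notes are screened in the six-month window. Code each of the two criteria as yes / no / not documented, on one proforma common to all sites.

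In section 5.4.7, report both the count and the UK projection as a range:

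- lower limit: women with both criteria documented yes;
- upper limit: women with no documented no on either criterion.

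Describe the result, and objective 4, as the number potentially eligible before exclusion criteria and consent. The range covers silent notes. It brackets the true number among the women screened only if the recorded yes and no entries are themselves correct, so code them from what the notes state and not from age or current inactivity.

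The cost is real but modest. Sites would log more women than section 5.4.6 now describes, with a few extra fields each, although these are women whose notes are already being read. The result is a range, possibly a wide one, in place of a single number.

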#### 5.4.6 DATA COLLECTION

Members of the women's direct care team will collect anonymised data on women meeting the eligibility criteria via scrutiny of referral letters and clinic notes. Sites will be asked to report these data a minimum of

once a month during the six-month data collection window, but can do this at a frequency (e.g., weekly, every two weeks) that suits their local clinical set up and resources. Data will be recorded in an anonymous screening log/proforma and sent securely to the C-POP research team at University of Birmingham. As part of the site initiation visits and study set up, the C-POP research team will work with the site to establish the best ways to record and send these data. Demographic information available in notes (e.g., age, ethnicity, first half of postcode (as a marker of deprivation) and first language) will also be collected to enable characterisation of the potential trial population.

#### 5.4.7 DATA ANALYSIS

GDPR-compliant data will be sent securely to the central C-POP team for collation and analysis using descriptive statistics. Using Birmingham Clinical Trials Unit's extensive knowledge of delivering Women's Health trials, data collected will be used to model the number of women across the UK likely to be eligible for recruitment into a future RCT [Core element 1&4: Context, Uncertainties].

## 5.5 Work package 4: National Stakeholder event to finalise the C-POP programme theory and recommendations for an effectiveness study (objective 5)

#### 5.5.1 DESIGN

National stakeholder event, guided by PPIE activities and [Core element 3: Stakeholders].

#### **5.5.2 TARGET POPULATION**

Stakeholders including women as per WP1; HCPs as per WP2; and other stakeholders who might be involved in a future effectiveness study (e.g., (but not limited to) clinical trials units, research and governance teams from potential sites, health economists, HTA representatives, CRNs etc.).

#### 5.5.3 SAMPLE SIZE

Anticipated 30-40 participants.

#### 5.5.4 SAMPLING AND RECRUITMENT

Women and HCPs who participate in WPs 1 and 2 will be invited to take part in the stakeholder event. We will contact them directly using the contact details they provided in WPs 1 and 2. If required, recruitment will be supplemented via the same recruitment pathways identified above in WPs1 and 2 (see sections 5.2.4 and 5.3.4).

Other stakeholders (e.g., health economists, CTU and CRNs) will be identified via professional bodies/membership of societies, adverts on social media, and via the research teams' personal and

professional networks and collaborators. Members of our PAG will also be invited.

#### 5.5.5 ELIGIBILITY

(*i*) Inclusion criteria: Women as per WP1, HCPs as per WP2. Other stakeholders who might be involved in a future effectiveness trial (see above), can converse in English, and who can give informed consent. (*ii*) Exclusion criteria: None. (*iii*) Rationale for eligibility criteria: This sample ensures we have inclusion of a wide range of stakeholders who can provide meaningful insight on our findings and potential future effectiveness trial delivery.

#### 5.6.6 CONSENT

Unless they participated in an earlier interview, participants in the workshop will be asked to complete a short demographic questionnaire to facilitate a description of participant characteristics. All participants in the workshop will complete a consent form prior to the start of the workshop. If the workshop is held remotely, the same pathways will be used as described for WP1 (see section 5.2.6).

#### 5.6.7 DATA COLLECTION

A one day in-person workshop (or remotely if needed), facilitated by the C-POP team and supported by our PPIE group, with discussions (small group and whole group) to encourage interaction between participants. Participants will be given the choice to see the main topics for discussion in advance of their participation, allowing participants to familiarise themselves and raise any queries with the team prior to or during the workshop. At the start of the workshop, we will present our proposed programme theory (revised following WPs 1-3) and initial recommendations for a potential future effectiveness trial. Participants will then be split into smaller discussion groups which will be facilitated by a member of the research team and/or PPIE members. The workshop will offer an opportunity for interaction and communication between participants to provide a non-judgemental and empowering environment where participants feel comfortable and valued enough to share their views and question those of others(53-55).

Discussions will focus on the participants' reflections of the proposed programme theory (see Figure 1) and recommendations for a future effectiveness trial. Views from each group will then be shared and discussed within the whole group with an aim to reach consensus/compromise and ultimately collectively develop the final programme theory, recommendations, and identify future actions following the completion of the C-POP study. Ideally, the workshop will be run face to face in an easily accessible location; however, it is anticipated that given the context of COVID that it may need to be run virtually using a video conferencing platform. This will still allow us to use breakout rooms and employ strategies to ensure everyone feels valued, enhance consensus building and minimise use of resources.

Participants will be offered a £75 voucher to thank them for their time and travel expenses, where appropriate will also be reimbursed.

**5.6.7 Data analysis**: Discussions will be audio recorded and transcribed. Data generated in the event will be compared to that from WPs1-3 to facilitate collaborative development of the final programme theory and recommendations for a future effectiveness study [Core element 3-6: Stakeholders, Uncertainties, Refinement and Economics].

#### 5.7 End of Study Definition

The end of the study will be defined as the point at which analysis, integration and interpretation of all work packages has been completed and the programme theory for a potential future clinical trial has been finalised. We anticipate this to be in study month 20 (November 2024), where the funding end date is study month 21 (December 2024). REC and the sponsor will be notified of end of study within 90 days of the programme theory being finalised, with a final report due to REC/Sponsor due 12 months after this end of study point. The Draft Final Report to the funder will be submitted within two weeks of the end of the study.

## 6 Ethical and Regulatory Considerations

#### 6.1 Assessment and Management of Risk

#### 6.1.1 RISK REGISTER

A risk register will be developed maintained by the study management team to assess risk(s) and implement actions to mitigate against or reduce risk(s). Risks will be rated as red (high), amber (medium) or green (low) based on the likelihood that the risk will occur and the potential impact of the risk on the study. The register will be reviewed on a regular basis by the research team as risks (actual and potential) and the associated rating will likely change throughout the study period. The risk register will also be a rolling agenda item for the SMG and SSG meetings. Risks will be categorised into three main sections:

- (1) general (e.g., staffing, ethics/governance approvals, subcontracting, COVID-19, resource constraints, time constraints, engagement of recruiters and stakeholders)
- (2) participant (e.g., recruitment of sites, identification, diversity of sample, recruitment, sensitivity of discussions, distress, eligibility, disclosure of potential harm, language, availability for interview/events, location of interview/events)

(3) researcher (e.g., sensitivity of discussions, distress, disclosure of harm, location and timing of data collection).

